### **First Clinic Visit**

Recruited subjects will meet with the study coordinator at the CRC to begin the informed consent process. The study coordinator, [name], will explain all study procedures as well as explain how to follow the low marine omega-3 diet, fill out daily intake and symptom logs, sensory evaluation forms, and the food frequency questionnaire.

If the subject agrees to participate, they will be given control beverages to consume during the run-in phase and forms including sensory evaluation, food frequency questionnaire, and daily intake and symptom logs. Finally, a preliminary blood sample will be taken from the participant to assess their usual levels of EPA and DHA in blood lipid pools before the washout.

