### **Study Phase**

After the run-in, the participants will then be randomized to the beverage or pill group. During the study phase, there will be three clinic visits to the Cancer Research Center. The visits will occur on day 0, 14, and 29. At each visit, blood will be drawn.

Additionally on days 1 and 28, they will perform a sensory evaluation on the beverage using provided forms. The second sensory evaluation will be used to determine if long-term consumption of the beverage impacted its perception.

Over the course of the 28 days, participants will complete daily intake and symptom logs to ensure compliance to the low marine omega-3 diet and study intervention as well as monitor adverse effects.

To ensure compliance during the study, participants will be asked to return empty beverage or pill containers and any that were not consumed. One to three extra beverages or pills will be given to estimate how many were consumed.

Participants will again be asked if they would like to receive email reminders detailing daily tasks.

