### **Internal and External Validity**

Subjects will be stratified by gender and randomized to the study arms to enhance study internal validity. Age, BMI, and initial EPA and DHA levels will be measured in all participants to ensure even distribution across study arms. If differences in these variables are found, they will be used as covariates in data modeling.

Efforts will be made to ensure a diverse sample of study participants by recruiting from various areas around campus and not just recruiting students. Women will represent 50% of the study participants. No participant will be excluded on the basis of race or ethnicity.

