### **Data Analysis**

All data analysis will be performed using SAS statistical software.

The impact of the algae oil form on the primary outcome of change in erythrocyte EPA and DHA concentration will be evaluated using analysis of variance (ANOVA). Covariates including BMI, height, weight, sex, age, ethnicity, and pre-trial and baseline levels of EPA and DHA will be evaluated using a forward selection procedure.

The influence of product type on secondary outcomes including EPA and DHA concentrations in other blood lipid pools will also be evaluated using ANOVA.

Compliance will be measured using the daily intake log and number of empty bottles, pills received at each clinic visit. The number of days that the beverage is consumed and any noncompliance with the marine omega-3 restricted diet divided by the number of total days will be used to report compliance.

Exploratory analyses including influence of algae oil vehicle on various blood lipids, hormones, and metabolites and the influence of diet on various variables may also be performed.

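### The secondary EPA and DHA outcomes are stated as concentrations compared by ANOVA, with no day-0 adjustment fixed in advance; baseline enters only if the arms are found to differ or, on a broad reading, through forward selection

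*Protocol*

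**What the plan says.** All of this is in the Protocol.

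- **Data Analysis, primary outcome.** The outcome is a change: "primary outcome of change in erythrocyte EPA and DHA concentration will be evaluated using analysis of variance (ANOVA"). A list of candidate covariates follows, in which "pre-trial and baseline levels of EPA and DHA will be evaluated using a forward selection procedure".
- **Data Analysis, secondary outcomes.** A separate paragraph reads: "The influence of product type on secondary outcomes including EPA and DHA concentrations in other blood lipid pools will also be evaluated using ANOVA". It does not mention change, a time point or a covariate. It also does not name the pools; Objectives lists them as PBMC, platelets and plasma besides erythrocytes.
- **Internal and External Validity.** "Age, BMI, and initial EPA and DHA levels will be measured in all participants to ensure even distribution across study arms". Then: "If differences in these variables are found, they will be used as covariates in data modeling". Neither sentence is limited to the primary outcome. The same section stratifies randomisation by gender.
- **Study Phase.** "The visits will occur on day 0, 14, and 29. At each visit, blood will be drawn".
- **First Clinic Visit.** Before the run-in, "a preliminary blood sample will be taken from the participant to assess their usual levels of EPA and DHA in blood lipid pools". Each participant therefore has two samples that precede the randomised product: one before the washout and one on day 0.

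**The concern.** The primary outcome is worded as a change and has a covariate procedure. The secondary outcomes are worded as concentrations and tested by product type. Taken at face value, the second sentence compares the arms without the day-0 value that everyone has.

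Habitual EPA and DHA intake differs between people. Regular fish eaters are not excluded, and the washout lasts two weeks, so some of that variation may still be present on day 0 and day 29. With about 10 evaluable people per arm, an unadjusted comparison leaves it all in the residual error. A pool could then miss a real vehicle difference, or show one that was there before the product was started. Objective A covers four lipid pools, and three of them depend on this sentence.

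**Working it through.** **1. The plan's own figure.** Sample size justification gives a 20% difference, SD 15%, alpha 0.05, power 0.80 and 10 per group. For a two-group ANOVA (equivalent to a two-sided t test), the noncentral t gives power 0.757 at 9 per group and 0.805 at 10, so 10 per group is reproduced. Adding 20% to 20 people gives 20 × 1.2 = 24, the stated total. None of this depends on the present point.

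**2. Inputs for the secondary pools.** n = 10 per arm and SD 15% come from Sample size justification. That SD is for erythrocyte DHA; no SD is given for the other pools, so its use here is an assumption. The day-0 to day-29 correlation r is not in the protocol either, so a range is shown. Variances are taken as equal at the two times.

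**3. Power for a 15% difference.**
- Unadjusted: SE = 15 × √(2/10) = 6.71, noncentrality 15/6.71 = 2.24, 18 df, power **0.56**.
- Day-0 ANCOVA: SE = 15 × √(1 − r²) × √(1 + 1/16) × √(2/10), 17 df. The factor 1 + 1/16 allows for chance imbalance in the covariate. A sex term would take one further df and is not included here.

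| r | Residual variance, ANCOVA / raw | SE | Noncentrality | Power at 15% | Detectable difference at 80% power |
|---|---|---|---|---|---|
| unadjusted | 1 | 6.71 | 2.24 | 0.56 | 19.9% |
| 0 | 1.00 | 6.91 | 2.17 | 0.53 | 20.6% |
| 0.3 | 0.91 | 6.60 | 2.27 | 0.57 | 19.6% |
| 0.5 | 0.75 | 5.99 | 2.51 | 0.66 | 17.8% |
| 0.7 | 0.51 | 4.94 | 3.04 | 0.82 | 14.7% |
| 0.8 | 0.36 | 4.15 | 3.62 | 0.93 | 12.3% |

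**4. Chance imbalance.** The day-0 difference between arms has SD √(2/10) = 0.447 in SD units. Hence P(|difference| > 0.5 SD) = 2 × [1 − Φ(0.5/0.447)] = 0.26.

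**5. Type I error, by simulation (100,000 trials, 10 per arm).**

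| | r = 0.5 | r = 0.7 | r = 0.8 |
|---|---|---|---|
| Unadjusted, all trials | 0.051 | 0.049 | 0.050 |
| Unadjusted, trials with day-0 imbalance > 0.5 SD | 0.096 | 0.134 | 0.157 |
| ANCOVA always, all trials | 0.050 | 0.051 | 0.049 |
| ANCOVA only if baseline p < 0.05 (assumed trigger) | 0.045 | 0.036 | 0.032 |

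A second simulation of 400,000 trials gave 0.094, 0.135 and 0.158 for the second row.

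**6. If a change score was meant.** Its variance relative to the raw value is 2(1 − r): 1.4 at r = 0.3, 1.0 at 0.5 and 0.6 at 0.7. It improves on the raw value only when r exceeds 0.5.

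**The case against.** The strongest reply is that the protocol does use baseline. A reader of the secondary sentence alone might infer that the day-0 value plays no part. Internal and External Validity does not support that: initial EPA and DHA become covariates when the arms are found to differ, with no restriction to the primary outcome. The covariate list in Data Analysis can also be read as covering both sets of outcomes. This stands, and it limits the point to the lack of a fixed adjustment.

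Nor does the protocol say that raw day-29 values will be compared. The word *also* may carry over the change-based model, and Objectives speaks of accumulation over time. This stands as well; the raw comparison is one reading. The other readings do not remove the problem:

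- The imbalance rule gives no threshold. It does not say whether initial means the pre-washout or the day-0 sample, although Data Analysis separates pre-trial from baseline levels. It does not say that each pool is adjusted for its own value. With an assumed p < 0.05 trigger, the procedure is conservative.
- Forward selection would choose among at least eight candidates in about 20 people.
- A change score is not stated for these outcomes.

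A third reply is that an SAP, not shown here, may settle the model. It may. But the protocol already states an outcome form, a test and a conditional covariate rule, and the point concerns what these say.

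Finally, the gain is not assured. At r = 0.3 it is negligible, and at r = 0 ANCOVA is slightly worse.

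**Conclusion.** The point holds as one about prespecification and precision. On each reading, day-0 adjustment of the secondary pools is absent, triggered by an observed imbalance, selected from the data, or replaced by an unstated change score.

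A reader might infer that the planned test has an inflated false-positive rate. It does not: overall type I error is 5%. The rates of about 9 to 10%, 13% and 16% (r = 0.5, 0.7, 0.8) apply only to the 26% of trials with a day-0 imbalance above 0.5 SD, and only if no adjustment is made. In some of those trials the imbalance rule might bring baseline in, depending on its unstated trigger.

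The loss of power is real from about r = 0.5 upwards: 0.56 against 0.66 at r = 0.5 and 0.82 at r = 0.7, for a 15% difference. These figures rest on 10 evaluable people per arm, the erythrocyte SD carried over to the other pools, and an assumed r. Severity is minor to moderate, since only secondary outcomes are affected.

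**What to change.** Replace the secondary-outcome sentence in Data Analysis with wording such as:

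> For each secondary pool (plasma, PBMC, platelets), EPA and DHA at day 29 will be compared between products by ANCOVA. Product type, sex (the stratification factor) and that pool's own day-0 value of the same fatty acid will always be included. These terms are not subject to forward selection or to the imbalance check under Internal and External Validity. Day-14 values may be analysed in the same way.

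No new samples or procedures are needed. The cost is one or two residual degrees of freedom per model, and a slight loss of power if r is near zero (0.53 against 0.56 for a 15% difference at r = 0, before the sex term).

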## I. Objectives

The goal of this study is to assess if docosahexaenoic acid (DHA) and eicosapentaenoic acid (EPA) accumulate in blood lipids to the same extent when consumed as a fortified beverage as opposed to a traditional capsule as well as assess compliance to daily consumption, tolerance and acceptability of a fortified soymilk beverage.

It is hypothesized that DHA and EPA levels will be equivalent in erythrocytes after 4 weeks of fortified soymilk consumption as compared to commercial capsules.

We propose the following objectives:

- A. Evaluate the effect of EPA and DHA matrix (beverage or capsule) on accumulation of EPA and DHA in lipid pools over 4 weeks of daily consumption.
  1. EPA and DHA levels will be measured in erythrocytes, peripheral blood mononuclear cells (PBMC), platelets, and plasma over time.
- B. Assess suitability of soymilk as a delivery vehicle for EPA and DHA.
  1. Compliance will be measured using daily intake logs and the return of empty and full bottles of soymilk or remaining capsules
  2. Tolerability will be monitored using a daily symptom journal.
  3. Sensory acceptability will be monitored initially and after 4 weeks of consumption to validate long term use of the fortified soymilk.

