## II. Background and Rationale

Research shows that fish oil and its component fatty acids EPA and DHA provide health benefits such as reducing the risk of cardiac death and lowering inflammation. Yet a large portion of the population is not consuming the recommended amount of fish due to high cost, dietary restrictions such as vegetarianism/veganism, concerns about high levels of mercury, general dislike, and other factors. Additionally, to meet the recommendations fish and fish oil production present sustainability challenges. A potential alternative is to utilize EPA and DHA from algae. Algae oil has performed equally to fish oil in several clinical studies and has been demonstrated as safe for consumption. These sustainable oils can be added to foods increasing the potential for fatty acids to counteract chronic disease and increasing access to general consumers.

Emulsification of omega-3 fatty acids and incorporation into food products have been shown in multiple studies to enhance short-term bioavailability of the oil. This pre-emulsification before digestion improves the rate and extent of incorporation into lipid pools. Some longer term studies of 4 weeks showed no difference or bioequivalence between algae or fish oil capsules and various fortified foods or microencapsulated oils. However, soymilk has not been assessed as a vehicle for EPA and DHA. Therefore, the bioavailability or bioequivalence to capsules needs to be measured. This study will offer valuable data showing that algae oil consumed in a soymilk matrix has the ability to alter lipid pools in the long term. This study will also provide preliminary data including compliance, sensory acceptability, and tolerability, validating the use of an algae oil fortified soymilk in future clinical studies.

Previously, our lab has developed, and optimized EPA and DHA fortified non-dairy plant milk beverages utilizing algae oil emulsions (food grade). Soymilk was chosen as the optimal vehicle due to its ability to mask some of the algae oil flavor, while maintaining stability of the fatty

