### *Sample size justification*

- The sample size (10 per group) was calculated based on a one way ANOVA with a meaningful mean difference of 20%, power of 0.80, alpha of 0.05, and a standard deviation of 15% based on literature values of erythrocyte DHA levels . The expected dropout rate is 20%. Therefore, 24 participants will be recruited.

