## **6. Daily Intake and Symptom Journal**

A daily intake journal will be used to assess compliance. Subjects will record if and when they consumed the beverage or pill each day. Additionally, they will record If and when they consumed any of the restricted foods such as fish or shellfish and how much. The final part to the daily log will include recording symptoms such as bad breath, nausea, or bloating.

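### The compliance formula puts beverage days and diet lapses over one divisor under the label of compliance, and leaves out capsule intake during the intervention

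*Protocol*

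**What the plan says.** Compliance is objective B.1 of the protocol, and there it covers both products: "Compliance will be measured using daily intake logs and the return of empty and full bottles of soymilk or remaining capsules". Section II (Background and Rationale) gives it a purpose, listing it among "preliminary data including compliance, sensory acceptability, and tolerability, validating the use of an algae oil fortified soymilk in future clinical studies".

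The Data Analysis section deals with it in two sentences. The first names the sources, again for both products: "Compliance will be measured using the daily intake log and number of empty bottles, pills received at each clinic visit". The second gives the formula. It takes the number of days on which the beverage is consumed and joins to it "any noncompliance with the marine omega-3 restricted diet divided by the number of total days will be used to report compliance". This second sentence does not mention the capsule.

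Elsewhere the protocol keeps product intake and diet apart. The section on the daily intake and symptom journal asks for product intake ("Subjects will record if and when they consumed the beverage or pill each day") and, as a further item, for lapses from the diet ("they will record If and when they consumed any of the restricted foods such as fish or shellfish and how much"). The Study Phase section likewise names the diet and the intervention as two things to comply with, and asks for returned containers of either product.

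**The concern.** The two terms in the formula run in opposite directions. Days of intake go up with good adherence, whereas diet noncompliance goes up with poor adherence. Placing both over one divisor under one label either lets lapses count in the participant's favour or presents a lapse rate as if it were adherence. The formula also names one product only, in a trial that randomizes to two.

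What is at stake is the reported result for objective B.1. It is meant to support use of the soymilk in later studies, and a comparison of compliance between beverage and capsule needs the same definition in both arms. Diet adherence is also of some interest in its own right, because the foods and supplements barred under the Low Marine Omega-3 Diet section are themselves sources of EPA and DHA.

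**Working it through.** The protocol states no compliance figure, so there is nothing to reproduce. The check applies the formula as written to illustrative participants.

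**Inputs**
- Intervention length T = 28 days (Study Phase).
- Run-in of two weeks, 14 days, when every participant drinks the control beverage (Run-in Phase). Data Analysis does not say whether these days belong to the total, so T = 14 + 28 = 42 is shown as an alternative.
- Assumption: lapses are counted in days. The protocol gives no unit.
- Assumption: the counts of beverage days (b) and lapse days (v) are illustrative.

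**Reading 1: one ratio, (b + v)/T, with T = 28**
- b = 28, v = 0: 28/28 = 100%.
- b = 24, v = 4: (24 + 4)/28 = 100%. Four missed servings are cancelled by four lapses, and the score equals that of a perfect participant.
- b = 28, v = 4: (28 + 4)/28 = 114%.

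With T = 42 the pattern is the same: (38 + 4)/42 = 100% and (42 + 4)/42 = 110%.

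**Reading 2: two ratios, b/T and v/T, with T = 28**
- Beverage: b = 24 gives 24/28 = 86%. This is a usable compliance figure.
- Diet: v = 4 gives 4/28 = 14%. That is noncompliance. Adherence is (28 − 4)/28 = 86%.

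Nothing exceeds 100% on this reading. With T = 42 the diet figures are 4/42 = 10% and 38/42 = 90%.

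**Capsule arm, either reading**
- Over T = 28, a participant who takes every capsule and has no lapse has no beverage days, so the literal result is 0/28 = 0%.
- Over T = 42, the same participant has 14 control-beverage days from the run-in, giving 14/42 = 33%.

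In both cases the 28 days of capsule intake do not enter the formula.

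**After separating the two measures (T = 28)**
- b = 28, v = 4: product 28/28 = 100%, diet 24/28 = 86%.
- b = 24, v = 4: product 24/28 = 86%, diet 24/28 = 86%.
- 28 capsule days, v = 0: product 28/28 = 100%, diet 28/28 = 100%.

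**The case against.** The best defence is that nobody would add the two terms. The sentence joins them with a conjunction and gives lapses no unit. The journal and the Study Phase section treat product and diet separately, and a figure above 100% would be noticed at once. This largely stands: two ratios is the more natural reading, and on it the beverage figure is sound. A reader might infer from the 114% that inflated compliance will be reported. The documents do not support that as a prediction; they support only that the sentence permits it.

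A second defence is that a 14% lapse rate carries the same information as 86% adherence, provided it is labelled as a lapse rate. That is true, but the sentence puts it under the label of compliance and gives no instruction to label it otherwise.

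A third is that the capsule is missing by a slip, since the preceding sentence, objective B.1, the journal and the Study Phase section all include it. That is probably so. A reader might infer that capsule compliance is not measured, but those same places show that the data are collected. Only the formula fails to use them. A reader might also infer that half of the participants (12 of 24 under equal allocation) drop out of the measure altogether. The text does not establish this: if the total includes the run-in, everyone has beverage days, and only capsule intake during the intervention is lost.

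It might finally be said that definitions of this kind belong in a statistical analysis plan. Fine detail does. Here, however, the protocol already states a formula, and a later plan that defined compliance correctly would contradict it.

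**Conclusion.** The point holds, at low severity. The formula for a named objective is wrong as written. On the less natural reading, lapses raise reported compliance (100% or 114% in the 28-day examples). On the more natural one, a noncompliance rate (14% in the example) stands where adherence (86%) is meant. On both, capsule intake during the intervention is omitted. The percentages rest on counting lapses in days, on the choice of total days, and on invented counts; the direction of the error does not depend on the invented counts.

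The consequence stops at the reporting of objective B.1. It would be going too far to say that the trial's main result is at risk. The primary ANOVA of erythrocyte EPA and DHA and the sample size calculation do not use this ratio, and the protocol ties no analysis set or compliance threshold to it. The logs and returned units allow correct figures to be computed for both arms.

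**What to change.** Replace the formula sentence in Data Analysis with:

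> Product compliance is the number of intervention days on which the assigned beverage or capsule was consumed, divided by the number of intervention days. Diet adherence is reported separately, as the number of days without a restricted food or supplement divided by the number of days. Both are reported by arm and are not combined.

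The handling of discontinuations, unlogged days and run-in days can be left to the statistical analysis plan. The cost is three sentences of wording. All inputs are already collected, so no visit, form or assay changes.
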